9.2 Protocol Deviations

Potential planned or unplanned protocol deviations noted during clinical monitoring will be documented by category (i.e., inclusion criteria, exclusion criteria, study drug, safety assessment, efficacy assessment, visit window, informed consent, prohibited medication, and other). All deviations will be reviewed, categorized, designated important or not important, and finalized prior to database lock. Important protocol deviations will be defined as those potentially impacting safety or efficacy assessments. Additional details of what will be considered important can be found in the Protocol Deviation Guidance document.

9.3 Study Day

Study day is defined relative to the date of the first dose of the study treatment. For assessments that occur after the first dose date, study day is calculated as (assessment date – the first dose date + 1). For assessments that occur prior to the first dose date, study day will be calculated as (assessment date – the first dose date); there is no Study Day 0.

Study Treatment

In this study, the study treatment refers to mocetinostat and/or durvalumab.

10.0 Interim Analyses

Tumor assessment is planned as per the Predictive Probability Design, after a first stage of enrollment, to decide whether or not a cohort should be stopped for lack of tumor response as detailed in [Section 6.2](#).

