#### 3.1 Phase 1 Study

The dose escalation phase of the study will employ the mTPI method will be employed in decision making concerning mocetinostat dose escalation ([Appendix 2](#)).

The mocetinostat dose levels planned for evaluation include 50, 70, and 90 mg TIW, depending on safety observations. In addition, if necessary, dose de-escalation of mocetinostat to 40 mg TIW may be undertaken.

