### **8.4.2 Reporting Requirements**

All SAEs must be reported within 24 hours of Investigator/site knowledge of the event, irrespective of the extent of available AE information, by faxing the SAE report to the Sponsor's pharmacovigilance representative designated in the Study Manual. The 24-hour timeframe also applies to additional new information (follow-up) on previously forwarded SAE reports and to the initial and follow-up reporting of exposure during pregnancy and exposure via breastfeeding. The need for an expedited report to regulatory authorities will be determined by the Sponsor and necessary reporting will be performed by the Sponsor. The Sponsor will notify study investigators of all Suspected, Unexpected (as judged against the Investigator Brochure) Serious Adverse Reaction (SUSAR) reports. The investigator is responsible for reporting all SUSARs to the IRB/EC.

All AE (including SAEs) must be documented in source documents and reported in the CRF. Please note that the CRF and SAE report forms may collect information in somewhat different formats. Where the requested data overlap in different formats, the information should be consistent between the two forms.

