### **9.1 Hypothesis and Sample Size**

#### **9.1.1 Phase 1**

Approximately 24 patients may be enrolled into the Phase 1 portion of the study and up to 261 patients will be enrolled into the Phase 2 portion. Precise sample size cannot be defined, as it is dependent on the number of dose escalations based on the mTPI method, and the number of patients enrolled in the expansion cohorts.

The mTPI method ([Ji-2013](#)) will be employed in decision making concerning dose escalation within each regimen investigated. The assumptions to be applied in establishing the mTPI methodology are:

- each specific regimen exploration will include up to 30 patients;
- the MTD is defined to have 0.25 probability of toxicity; and

- the acceptable variance around the MTD is  $\pm 0.05$  (i.e., the region of the MTD is 20% to 30% incidence of dose limiting toxicity).

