### **9.7 Interim Analysis**

No interim statistical analysis is planned during this study.

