### **10.2 Obligations of Investigators**

The Investigator is responsible for complying with the protocol and all applicable regulations and guidelines governing clinical research. Additionally, he/she is responsible for ensuring that all participating staff members are adequately trained and competent to perform his/her assigned tasks.

All Investigators must provide the sponsor with a current *curriculum vitae*. Only Investigators and designated Sub-Investigators are permitted to sign CRFs and examination findings (e.g., laboratory results or ECGs).

The Investigator or designee is responsible for informing the patient of all available information relevant to his/her safety and obtaining signed, written consent from all participating patients. Additionally, the Investigator is responsible for monitoring patient safety and providing periodic and requested reports to the IRB/EC.

The Investigator is responsible for the accuracy and completeness of all study records including CRFs, source documents, and the Site Trial Master File. The Investigator will allow the study monitor, Sponsor, auditor, regulatory agencies, and IRB/EC full access to the study and source documents.

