### **14.3 Premature Termination**

Premature termination of this study may occur at any time because of a regulatory authority decision, change in opinion of the IRB/EC, drug safety concerns, or at the discretion of the Sponsor. In addition, the Sponsor retains the right to discontinue development of mocetinostat and durvalumab at any time. If termination becomes necessary, the Sponsor will inform the appropriate regulatory authorities of the termination and the reason. The Principal Investigator will inform the IRB/EC of the same. In terminating the study, the Sponsor and the Principal Investigator will assure that adequate consideration is given to the protection of the patients' interests.

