### Appendix 2. Dose-Finding Spreadsheet of the Modified Toxicity Probability Interval (MTPI) Method

Number of Dose Limiting Toxicities	Number of Patients Treated at Current Dose																														
	1	2	3	4	5	6	7	8	9	10	11	12	13	14	15	16	17	18	19	20	21	22	23	24	25	26	27	28	29	30	
0	E	E	E	E	E	E	E	E	E	E	E	E	E	E	E	E	E	E	E	E	E	E	E	E	E	E	E	E	E	E	
1	D	S	S	S	S	S	E	E	E	E	E	E	E	E	E	E	E	E	E	E	E	E	E	E	E	E	E	E	E	E	
2		U	D	D	S	S	S	S	S	S	S	S	S	E	E	E	E	E	E	E	E	E	E	E	E	E	E	E	E	E	
3			U	U	U	D	S	S	S	S	S	S	S	S	S	S	S	S	S	E	E	E	E	E	E	E	E	E	E	E	
4				U	U	U	U	U	D	S	S	S	S	S	S	S	S	S	S	S	S	S	S	S	S	S	E	E	E	E	
5					U	U	U	U	U	U	D	S	S	S	S	S	S	S	S	S	S	S	S	S	S	S	S	S	S	S	
6						U	U	U	U	U	U	U	U	D	S	S	S	S	S	S	S	S	S	S	S	S	S	S	S	S	
7							U	U	U	U	U	U	U	U	U	S	S	S	S	S	S	S	S	S	S	S	S	S	S	S	
8								U	U	U	U	U	U	U	U	U	U	U	U	S	S	S	S	S	S	S	S	S	S	S	
9									U	U	U	U	U	U	U	U	U	U	U	U	S	S	S	S	S	S	S	S	S	S	
10										U	U	U	U	U	U	U	U	U	U	U	U	U	U	U	U	S	S	S	S	S	
11											U	U	U	U	U	U	U	U	U	U	U	U	U	U	U	U	U	U	S	S	
12												U	U	U	U	U	U	U	U	U	U	U	U	U	U	U	U	U	U	U	
13													U	U	U	U	U	U	U	U	U	U	U	U	U	U	U	U	U	U	
14														U	U	U	U	U	U	U	U	U	U	U	U	U	U	U	U	U	
15															U	U	U	U	U	U	U	U	U	U	U	U	U	U	U	U	
16																U	U	U	U	U	U	U	U	U	U	U	U	U	U	U	
17																	U	U	U	U	U	U	U	U	U	U	U	U	U	U	
18																		U	U	U	U	U	U	U	U	U	U	U	U	U	
19																			U	U	U	U	U	U	U	U	U	U	U	U	
20																				U	U	U	U	U	U	U	U	U	U	U	
21																					U	U	U	U	U	U	U	U	U	U	
22																						U	U	U	U	U	U	U	U	U	
23																							U	U	U	U	U	U	U	U	
24																								U	U	U	U	U	U	U	
25																									U	U	U	U	U	U	
26																										U	U	U	U	U	
27																												U	U	U	
28																													U	U	
29																														U	U
30																															U

**E** = Escalate to the next higher dose  
**S** = Stay at the current dose  
**D** = De-escalate to the next lower dose  
**U** = The current dose is unacceptably toxic  
MTD = 0.25  
Sample Size = 30  
 $\epsilon_1 = 0.05$   
 $\epsilon_2 = 0.05$

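### Phase 2 states no count or rate of toxicity at which enrolment pauses; the numeric DLT rule covers Phase 1 only, and the one formal Phase 2 stop is for lack of response

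*SAP*

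**What the plan says.** **Phase 1.** Protocol 3.1 says the modified toxicity probability interval method "will be employed in decision making concerning mocetinostat dose escalation". Protocol 9.1.1, headed Phase 1, sets the target at 0.25 and adds that "the region of the MTD is 20% to 30% incidence of dose limiting toxicity". Appendix 2 turns this into a table of DLTs by patients treated, with U meaning "The current dose is unacceptably toxic". Protocol 9.3.4 defines DLT-evaluable patients for dose-escalation decisions.

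**Phase 2 efficacy look.** SAP 10.0 describes a tumour assessment after the first stage of enrolment, "to decide whether or not a cohort should be stopped for lack of tumor response". Protocol 9.7 says "No interim statistical analysis is planned during this study", and 9.8 plans no data monitoring committee. Protocol 9.3.2 and SAP 7.3 remove patients who stop for an adverse event or toxicity before their first on-study scan from the population used for this decision. Expansion of Cohorts 3 and 4 to as many as 100 patients each depends on efficacy interest (Protocol 9.1.2).

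**Phase 2 safety handling.** Protocol 5.1.8, 5.2.8 and Appendix 4 give patient-level holds, dose reductions and discontinuations. Protocol 8.4.2 says "All SAEs must be reported within 24 hours of Investigator/site knowledge of the event", and 8.3.3.2 sends all pericardial findings to the sponsor by the same expedited procedure, for Medical Monitor review. Protocol 10.2 says that "the Investigator is responsible for monitoring patient safety and providing periodic and requested reports to the IRB/EC". Under Protocol 14.3 the study may be ended because of "a regulatory authority decision, change in opinion of the IRB/EC, drug safety concerns, or at the discretion of the Sponsor".

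**The concern.** The sponsor has already decided what DLT experience it would call unacceptable, and has printed it. That judgement lapses when Phase 2 begins, although Phase 2 is planned for up to 261 patients against about 24 in Phase 1 (Protocol 9.1.1). The one formal Phase 2 rule takes no toxicity input. A patient lost early to toxicity does not count in it, and because stage sizes are stated in evaluable patients, the cohort must enrol someone else to reach 9 or 17.

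Protocol 1.4 describes the two safety profiles as mostly non-overlapping. It also warns that mocetinostat could worsen durvalumab's immune-related events and that cystitis and pericardial risk may rise with the combination. If an excess appeared, individual patients would be managed by rule, but whether to keep enrolling would rest on discretion alone. At stake is how quickly, and on what agreed basis, enrolment is paused.

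**Working it through.** **1. The plan's own Phase 2 figures.** For stage 1 size n1 with continuation bound a, and total n with success bound r, the probability of success is the sum over x ≥ a of P(x of n1) × P(at least r−x of n−n1).

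- Cohorts 1, 3 and 4 (9 then 17; bounds 1 and 3; rates 5% and 30%): early termination 0.95^9 = 0.630, Type 1 error 0.0466, power 0.9045.
- Cohort 2 (17 then 44; bounds 5 and 18; rates 27% and 50%): 0.498, 0.0303, 0.9018.

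These agree with Protocol 9.1.2. The formula contains only the response rate. At the target rate a cohort passes Stage 1 with probability 1−0.7^9 = 0.96 (n1 = 9) or 0.975 (n1 = 17). The maximum of 17+44+100+100 = 261 also agrees.

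**2. Appendix 2 entries at n = 6, 12, 18, 24 and 30.** Posterior Beta(1+x, 1+n−x), a uniform prior; U if P(rate > 0.25) exceeds 0.95. The prior and the 0.95 cut-off are assumptions, since the documents print only the table.

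| n | First U count | P(rate > 0.25) there | P(rate > 0.25) one DLT fewer |
|---|---|---|---|
| 6 | 4 | 0.987 | 0.929 |
| 12 | 6 | 0.976 | 0.920 |
| 18 | 8 | 0.971 | 0.923 |
| 24 | 10 | 0.970 | 0.929 |
| 30 | 12 | 0.971 | 0.936 |

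The printed table gives the same U bounds in these five columns, which are the only ones used here. The only D (de-escalate) entry in them is 3 of 6.

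**3. How often a pause at these bounds would occur.** The documents give no DLT rate for the combination, so every true rate p below is assumed. Each block of 6 patients adds a Binomial(6, p) count; sequences at or above the bound are removed as paused, and the rest carry on. First look at p = 0.40: 15(0.4^4)(0.6^2) + 6(0.4^5)(0.6) + 0.4^6 = 0.138 + 0.037 + 0.004 = 0.179. Continuing the recursion (entries rounded separately):

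| True DLT rate | n=6 | n=12 | n=18 | n=24 | n=30 | Any pause |
|---|---|---|---|---|---|---|
| 20% | 0.017 | 0.013 | 0.007 | 0.004 | 0.002 | 0.044 |
| 25% | 0.038 | 0.035 | 0.024 | 0.016 | 0.012 | 0.124 |
| 30% | 0.071 | 0.074 | 0.054 | 0.041 | 0.031 | 0.270 |
| 40% | 0.179 | 0.190 | 0.134 | 0.096 | 0.071 | 0.670 |
| 50% | 0.344 | 0.296 | 0.158 | 0.085 | 0.048 | 0.931 |

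Mean DLT-evaluable patients when a pause occurs: 15.2 at 40% and 12.8 at 50%. For example, at 40%: (6×0.179 + 12×0.190 + 18×0.134 + 24×0.096 + 30×0.071)/0.670 ≈ 15.2.

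**4. The 3-of-6 entry.** 20p³(1−p)³ = 0.08, 0.13, 0.19, 0.28 and 0.31 at the five rates. A review at 3 of 6 with no later pause has probability 0.07, 0.09, 0.10, 0.06 and 0.01.

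**5. Scale.** At a 40% rate, 30 × 0.40 = 12 DLTs are expected in 30 DLT-evaluable patients, which is the table's own U bound.

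**The case against.** The strongest reply is that this is a permitted design choice. The study is open-label, the sponsor sees toxicity accrue, and Protocol 14.3 allows termination for safety at any time. That stands, and it is why nothing here is called an error.

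Two stronger readings are tempting, and the documents support neither.

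- A reader might infer that excess toxicity in Phase 2 would prompt no action. It would prompt a good deal: any immune-related event interrupts mocetinostat, Grade 4 immune-related events generally end durvalumab, moderate or large pericardial effusions mean immediate removal from treatment, and serious events reach the sponsor within 24 hours. What is missing is only an enrolment-level number.
- A reader might infer that Phase 1 readily passes a toxic dose, because the MTD can rest on 6 patients and 0 to 2 DLTs in 6 has probability 0.74, 0.54 and 0.34 at true rates of 30%, 40% and 50%. But Phase 2 uses the RP2D, which may sit below the MTD and must also show no related Grade 3 or higher or serious immune-related event and adequate dose intensity (Protocol 3.1.4). Adding an assumed earlier look at 3 patients, and assuming that 25% to 50% of DLT patients have such an event, the chance of passing is at most 0.33 to 0.20 at 40% and 0.19 to 0.11 at 50%. The dose-intensity criterion cannot be computed and would lower it further.

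Objections to the remedy also have force. A Cycle 1 DLT count largely misses the harms Protocol 1.4 names: immune colitis began 43 to 138 days after the first durvalumab dose, and Protocol 1.2.3 places cystitis mostly after several cycles. The rule pauses 27% of the time at a 30% rate, the edge of the accepted region, and never pauses in 33% of sequences at 40%. Restarting still rests with the sponsor. These limit what the rule can achieve, but they do not supply the missing number.

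**Conclusion.** The gap is real and modest. Neither document gives a Phase 2 count or rate of toxicity at which enrolment pauses, and the one formal Phase 2 decision excludes early toxicity dropouts. No stated figure is wrong and all the Phase 2 efficacy figures reproduce, so this is a cheap safety improvement rather than a correction.

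Its size depends wholly on assumed DLT rates. Reusing the sponsor's table would pause enrolment with probability 0.67 at a 40% rate and 0.93 at 50%, after about 15 and 13 DLT-evaluable patients on average, against 0.04 at 20% and 0.12 at the 25% target. The calculation assumes independent patients, a constant rate across cohorts and complete Cycle 1 data at each look. A reader might also infer that the trial needs a data monitoring committee; nothing in the documents establishes that, and the change below does not require one.

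**What to change.** Add to Protocol 3.2 and 9.7 and to SAP 10.0:

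- Cycle 1 DLTs (Protocol 3.1.1) at the RP2D are counted across all Phase 2 cohorts.
- The Medical Monitor reads the cumulative count against Appendix 2 after 6, 12, 18, 24 and 30 DLT-evaluable Phase 2 patients (Protocol 9.3.4).
- A U entry, meaning at least 4, 6, 8, 10 or 12 DLTs respectively, pauses new enrolment until a documented sponsor review is complete.
- A count of 3 in 6 prompts a documented review without a pause.
- At each look, three items are tabulated over all cycles: related Grade 3 or higher or serious immune-related events, pericardial events, and early discontinuations for toxicity.

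**Cost.** Protocol and SAP wording and five short reviews, using a table, DLT definition and Medical Monitor already in place. The efficacy design is unchanged. An unneeded pause has probability 4%, 12% and 27% at DLT rates of 20%, 25% and 30%; a review at 3 of 6 with no later pause adds 7%, 9% and 10%. A pause is for review and does not terminate the study.

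**Limits to state in the text.** Late immune-related events and cystitis have no numeric trigger, the table ends at 30 patients, and patients enrolled while Cycle 1 data mature come on top of the counts above.

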11.0 Data Review

Beyond the data screening built into the PRA Data Management Plan, the PRA programming of analysis datasets, tables, figures, and listings (TFL) provides additional data screening. Presumed data issues will be output into SAS logs identified by the word “Problem” and extracted from the logs by a SAS macro and sent to PRA Data Management.

Review of a pre-freeze TFL run on clean patients and a post-freeze TFL run on the frozen database allow for further data screening prior to lock. The post-freeze TFLs will be discussed with the sponsor in a data review meeting to identify any final data issues and seek corrections prior to database lock. The PRA statistician and the sponsor must approve database lock.

12.0 Statistical Methods

All data collected during this study will be displayed in data listings, unless otherwise specified. Data listings will be sorted by dose level and patient identifier (regardless of phase) for safety listings and by

Sponsor: Mirati Therapeutics, Inc.

Protocol no: 0103-020

phase, dose level/cohort, and patient identifier for efficacy. Screen failures will be excluded from all tables and listings. In addition, listings will include all relevant derived variables.

Descriptive statistics (mean, median, standard deviations [STD], minimum and maximum values) for continuous variables will be presented. Mean and median will be presented to 1 decimal more than original data. STD will be presented to 2 decimals more than original data. Minimum and maximum will match the decimal points in the original data. For categorical variables, summary measures will include the frequency and percentage (with 1 decimal place) of patients in each category.

The summary tables will be presented by dose level (both phases combined) for safety and by phase and dose level/cohort for efficacy.

Unless otherwise noted, missing data will not be imputed or carried forward.

All data summaries and tabulations will be prepared with SAS® Version 9.4 or higher.

12.1 Patient Disposition

The number and percentage of patients enrolled and treated in the study will be presented, together with the number and percentage of patients who withdrew from the study prematurely and a breakdown of the corresponding reasons for withdrawal and the number and percentage of patients who discontinued mocetinostat and durvalumab with the corresponding reasons. will be reported by category for each phase and dose level/cohort, as well as overall within each phase. Additionally the number of patients in the mITT, Clinical activity evaluable, Safety, and DLT Evaluable populations will be presented.

12.2 Important Protocol Deviations

Important protocol deviations (see definition in [Section 9.2](#)) for patients in the Enrolled Population will be reported by category for each study arm. Important protocol deviations will be listed.

12.3 Treatments

12.3.1 Extent of Study Treatment Exposure

Exposure to treatment will be summarized by dose level for the Safety population separately for mocetinostat and durvalumab. Descriptive statistics will be provided for the duration of exposure (weeks), the total number of cycles started, number of doses received, cumulative dose received (mg) and dose intensity (mg/week).

Number and percentage of patients with at least 1 dose reduced (only for mocetinostat), at least 1 dose interrupted and reasons for dose reduction and interruption will be presented separately for mocetinostat and durvalumab.

Information regarding patients' dosing regimens will be listed separately for mocetinostat and durvalumab.

12.3.2 Concomitant Medications

Concomitant medications will be coded using World Health Organization (WHO) Drug Enhanced (version: March 2016).

Prior and concomitant medications will be tabulated separately for the Enrolled population by dose level Anatomical Therapeutic Chemical Classification and preferred drug name using counts and percentages. The number and percentage of patients using at least one medication within each dose level will also be displayed. See [Section 8.3.5](#) for the definition of concomitant medications.

Prior and concomitant medications will be included in a patient data listing.

Sponsor: Mirati Therapeutics, Inc.

Protocol no: 0103-020

12.4 Demographic and Baseline Characteristics

Demographic and baseline data will be summarized descriptively by phase and by dose level/cohort and overall within each phase for the Safety population. For continuous variables, descriptive statistics will include the mean, STD (or standard error), median, range, and interquartile range. For categorical variables, descriptive statistics will include the number and percent.

Demographic variables to be summarized include age (years), gender, reproductive status for female, ethnicity, race, weight (kg), height (m), smoking history and Eastern Cooperative Oncology Group (ECOG) status.

Medical history will be tabulated by system organ class (SOC) and preferred term (PT) using counts and percentages for the Safety population.

Primary Disease history will be tabulated for the Safety population and include the summary statistics (count and percentage) for Histology (Adenocarcinoma, squamous Cell Carcinoma, Large Cell Carcinoma and Other) and Current Stage (Locally Advanced, Metastatic).

Prior Primary Disease Treatment (Systemic therapy, radiotherapy and surgery) will be tabulated for the Safety population and include the summary statistics (count and percentage) for the following:

- Prior Systemic therapy - Platinum agent received (Cisplatin, Carboplatin, Other), Regimen (Neo-Adjuvant or Adjuvant, Advanced Disease Treatment Regimen, Other), Prior checkpoint inhibitor use (Nivolumab, Pembrolizumab, Durvalumab, Other)
- Prior radiotherapy – Type (Adjuvant, Palliative))
- Prior surgery – Location (Lung, Liver, Lymph Node, Adrenal, Brain, Other)

Demographic, medical history, primary disease history, and prior primary disease treatment data will be listed by patient.

12.5 Efficacy Analyses

12.5.1 ORR, Best Overall Response and CBR

Descriptive statistics (frequency and percentage) for ORR, CBR and of best overall response (CR, PR, SD, PD) based on the Response Assessments by the Investigator and the exact 95% Clopper-Pearson confidence interval (SAS® PROC FREQ) of the response rate will be presented by phase and by dose level/cohort and overall within each phase. An exact test (SAS® PROC FREQ) for single proportion (two-sided $\alpha=5\%$) will be performed to test H_0 : ORR $\leq 5\%$ against H_1 : ORR $> 5\%$ in cohorts 1, 3, and 4 and to test H_0 : ORR $\leq 27\%$ against H_1 : ORR $> 27\%$ in cohort 2, for phase 2 of the study. Patients who cannot be assessed for response will be counted as non-responders. Descriptive statistics (frequency and percentage) for CR and PR rate will be presented by phase, dose level/cohort, and overall within each phase. In addition, exact binomial 95% CIs for the percentage will be displayed for CR and PR rate, respectively.

The primary analyses will be conducted in the clinical activity evaluable population. Supportive analyses will be presented in the mITT population.

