### **9.1.2 Phase 2**

The 4-cohort Phase 2 portion uses sample sizes based on Predictive Probability Design (Lee-2008). ORR in accordance with RECIST 1.1 is the primary clinical benefit endpoint. In creating the statistical designs, the Type 1 error ( $\alpha$ ) is constrained to  $<0.05$  and Power ( $1-\beta$ ) is constrained to  $\geq 0.90$ .

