#### **Statistical Design Applied to Phase 2 Cohorts 1, 3 and 4**

The ORR using a PD-L1 inhibitor in the population with advanced NSCLC having no or low PD-L1 expression, or prior disease progression on a checkpoint inhibitor, is assumed to be 5% ( $p_0$ ); thus this rate is considered uninteresting. The target ORR using mocetinostat in combination with durvalumab in this study is 30% ( $p_1$ ). Stage 1 of enrollment will include a minimum of 9 evaluable patients. With exactly 9 evaluable patients at Stage 1, if at least 1 patient has an Objective Response, 8 additional evaluable patients will be enrolled, for a total sample size of 17 evaluable patients. If at least 3 Objective Responses are observed, further investigation may be warranted. If the true ORR is 5% (null hypothesis), the probability of early termination during the study is 0.63; the Type 1 error is equal to 0.0466 and the power is equal to 0.9045.

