#### **Statistical Design Applied to Phase 2 Cohort 2**

The ORR using a PD-L1 inhibitor in the population with advanced NSCLC having high PD-L1 expression is assumed to be 27% ( $p_0$ ); thus this rate is considered uninteresting. The target ORR using mocetinostat in combination with durvalumab in this study is 50% ( $p_1$ ). Stage 1 of enrollment will include approximately 17 evaluable patients. With exactly 17 evaluable patients at Stage 1, if at least 5 patients have Objective Responses, 27 additional evaluable patients will be enrolled, for a total sample size of 44 evaluable patients. If at least 18 Objective Responses are observed, further investigation may be warranted. If the true ORR is 27% (null hypothesis), the probability of early termination during the study is 0.50; the Type 1 error is equal to 0.0303 and the power is equal to 0.9018.

The exact stopping rules for all cohorts will be calculated based on the Predictive Probability Design, once the exact number of patients evaluable at Stage 1 is known. The aim is to get about 9 evaluable patients at Stage 1 for cohorts 1, 3 and 4 and about 17 evaluable patients at Stage 1 for cohort 2.

If Stage 2 results in Cohorts 3 and 4 are of high interest for efficacy, enrollment may be expanded to as many as 100 patients total in each cohort to narrow the 95% Confidence Interval (CI) around the ORR point estimate. Table 14 presents estimates of the 95% CI around the observed ORR for several potential outcomes using the sample size of 100 patients, and the Clopper-Pearson method.

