## **9.4 Efficacy Endpoint Definitions and Analyses**

### **9.4.1 Objective Response Rate**

Objective disease response will be categorized in accordance with RECIST v1.1 ([Appendix 5](#)). Objective Response Rate (ORR) is defined as the percent of patients documented to have a confirmed Complete Response (CR) or Partial Response (PR). If central review of disease response is undertaken, ORR as reported by the central

radiology review laboratory will be used to calculate ORR and the exact 95% confidence intervals (CI). ORR as reported by the investigator will be used in study expansion decision making (Predictive Probability design) and supportive analyses.

Descriptive statistics (frequency and percentage) for ORR, CR, and PR will be presented. The exact 95% CI of these response rates will be calculated. An exact test for single proportion (two-sided  $\alpha=5\%$ ) will be performed to test  $H_0$ : ORR  $\leq 5\%$  against  $H_1$ : ORR  $> 5\%$  in cohorts 1, 3 and 4 and to test  $H_0$ : ORR  $\leq 27\%$  against  $H_1$ : ORR  $> 27\%$  in cohorts 2. Other details will be described in the SAP.

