6.3 Sample Size Considerations

6.3.1 Phase 1

Approximately 24 patients may be enrolled into the Phase 1 portion of the study. A precise sample size cannot be defined, as it is dependent on the number of dose escalations based on the mTPI method.

The mTPI method ([Ji 2013](#)) will be employed in decision making concerning dose escalation within each regimen investigated. The assumptions to be applied in establishing the mTPI methodology are:

- Each specific regimen exploration will include up to 30 patients
- The MTD is defined to have 0.25 probability of toxicity; and
- The acceptable variance around the MTD is ± 0.05 (i.e., the region of the MTD is 20% to 30% incidence of DLT).

6.3.2 Phase 2

Up to 261 patients may be enrolled into the Phase 2 portion of the study.

The 4-cohort Phase 2 portion uses sample sizes based on Predictive Probability Design (Lee-2008). ORR in accordance with RECIST 1.1 is the primary clinical benefit endpoint. In creating the statistical designs, the Type 1 error (α) is constrained to <0.05 and Power ($1-\beta$) is constrained to ≥ 0.90 .

6.3.3 Statistical Design Applied to Phase 2 Cohorts 1, 3 and 4

The ORR using a PD-L1 inhibitor in the population with advanced NSCLC having no or low PD-L1 expression, or prior disease progression on a checkpoint inhibitor, is assumed to be 5% (p_0); thus this rate is considered uninteresting. The target ORR using mocetinostat in combination with durvalumab in this study is 30% (p_1). Stage 1 of enrollment will include a minimum of 9 evaluable patients per cohort. With exactly 9 evaluable patients at Stage 1, if at least 1 patient has an Objective Response, 8 additional evaluable patients will be enrolled, for a total sample size of 17 evaluable patients. If at least 3 Objective Responses are observed, further investigation may be warranted. If the true ORR is 5% (null hypothesis), the probability of early termination during the study is 0.63; the Type 1 error is equal to 0.0466 and the power is equal to 0.9045.

Sponsor: Mirati Therapeutics, Inc.

Protocol no: 0103-020

6.3.4 Statistical Design Applied to Phase 2 Cohort 2

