The ORR using a PD-L1 inhibitor in the population with advanced NSCLC having high PD-L1 expression is assumed to be 27% (p_0); thus this rate is considered uninteresting. The target ORR using mocetinostat in combination with durvalumab in this study is 50% (p_1). Stage 1 of enrollment will include approximately 17 evaluable patients. With exactly 17 evaluable patients at Stage 1, if at least 5 patients have Objective Responses, 27 additional evaluable patients will be enrolled, for a total sample size of 44 evaluable patients. If at least 18 Objective Responses are observed, further investigation may be warranted. If the true ORR is 27% (null hypothesis), the probability of early termination during the study is 0.50; the Type 1 error is equal to 0.0303 and the power is equal to 0.9018.

The exact stopping rules for all cohorts will be calculated based on the Predictive Probability Design, once the exact number of patients evaluable at Stage 1 is known. The aim is to get about 9 evaluable patients at Stage 1 for cohorts 1, 3 and 4 and about 17 evaluable patients at Stage 1 for cohort 2.

If Stage 2 results in Cohorts 3 and 4 are of high interest for efficacy (as decided by the sponsor), enrollment may be expanded to as many as 100 patients total in each cohort to narrow the 95% Confidence Interval (CI) around the ORR point estimate.

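### At 17 evaluable patients the planned two-sided exact test of ORR needs 4 responses, one above the go boundary of 3, so its power is about 0.79 and not the stated 0.90; Cohort 2 has a smaller gap that depends on how the p-value is defined

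*SAP*

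**What the plan says.** Protocol 9.1.2 sets the design limits in the sentence that opens "In creating the statistical designs, the Type 1 error": alpha below 0.05 and power at least 0.90. For Cohorts 1, 3 and 4 (null 5%, target 30%; 9 patients, continue on at least 1 response, 17 in total) it reports that "the Type 1 error is equal to 0.0466 and the power is equal to 0.9045". For Cohort 2 (null 27%, target 50%; 17 patients, continue on at least 5, 44 in total) it reports that "the Type 1 error is equal to 0.0303 and the power is equal to 0.9018". SAP 6.3 repeats both designs and attaches the figures to these boundaries: "If at least 3 Objective Responses are observed, further investigation may be warranted" and "If at least 18 Objective Responses are observed, further investigation may be warranted".

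The final analysis is specified elsewhere. Protocol 9.4.1 plans "An exact test for single proportion (two-sided", alpha 5%) of the same null rates against the one-directional alternative that ORR is higher. SAP 12.5.1 repeats the test as "An exact test (SAS® PROC FREQ) for single proportion (two-sided", alpha 5%), and adds an "exact 95% Clopper-Pearson confidence interval". Neither document gives the critical count or the power of this test, or says how its two-sided p-value is formed.

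**The concern.** Two procedures address the same null hypotheses in the same cohorts, and operating characteristics are given for only one. The go rule is one-sided and two-stage. The reported test is single-stage at two-sided 5%, which is stricter. If the test needs more responses than the go boundary, its power is below the figure printed beside p0 and p1. A cohort that just reaches the boundary would then be reported as not significant, and nothing in the plan prepares the reader for it. This is the only planned test of the primary Phase 2 endpoint, so its power is what a reader of the results will want to know.

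**Working it through.** **Inputs.** Null and target rates, stage sizes and boundaries come from Protocol 9.1.2 and SAP 6.3. Sidedness, alpha and interval come from Protocol 9.4.1 and SAP 12.5.1. X_n denotes a binomial count in n patients. The Stage 1 stop is kept throughout.

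**1. Reproduce the stated figures, Cohorts 1, 3 and 4.** A go needs at least 3/17 with at least 1/9 at Stage 1, so P(go) = P(X_17 ≥ 3) − P(X_9 = 0) × P(X_8 ≥ 3).

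- ORR 5%: 0.05025 − 0.63025 × 0.00579 = 0.0466. Early stopping: 0.95^9 = 0.630.
- ORR 30%: 0.92261 − 0.04035 × 0.44823 = 0.9045.

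Both agree with the plan.

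**2. Apply the planned test at 17 patients.** Under 5%, the probabilities of 0, 1 and 2 responses are 0.41812, 0.37411 and 0.15752, so the upper tail at 3 is 1 − 0.94975 = 0.0503. Minimum likelihood adds nothing, because P(0), P(1) and P(2) all exceed P(3) = 0.0415.

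| Result | One-sided | Doubled tail | Minimum likelihood | 95% Clopper-Pearson |
|---|---|---|---|---|
| 3/17 | 0.0503 | 0.1005 | 0.0503 | 3.8–43.4% |
| 4/17 | 0.0088 | 0.0176 | 0.0088 | 6.8–49.9% |

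At 3/17 no version reaches 0.05 and the interval contains 5%. The test first rejects at 4/17.

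**3. Operating characteristics of the test (at least 4/17).** Use the formula of step 1 with 4 in place of 3.

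- Alpha: 0.00880 − 0.63025 × 0.00037 = 0.0086.
- Power at 30%: 0.79809 − 0.04035 × 0.19410 = 0.790.
- Go but not significant, at 30%: 0.90453 − 0.79026 = 0.114. As a share of go results: 0.11427 / 0.90453 = 12.6%, about one in eight.

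**4. Cohort 2.** Here P(go) is the sum over Stage 1 counts x = 5 to 17 of P(X_17 = x) × P(X_27 ≥ 18 − x). It gives alpha 0.0303, power 0.9018 and early stopping 0.498, again in agreement with the plan.

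| Result | One-sided | Doubled tail | Minimum likelihood | 95% Clopper-Pearson |
|---|---|---|---|---|
| 18/44 | 0.0317 | 0.0635 | 0.0423 | 26.3–56.8% |
| 19/44 | 0.0150 | 0.0300 | 0.0255 | 28.3–59.0% |

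The minimum-likelihood value at 18/44 adds P(X ≤ 5) = 0.0105 to 0.0317. By doubled tail, or by whether the planned interval excludes 27%, the test needs 19/44: alpha 0.0146 and power 0.847. A go without significance then has probability 0.90177 − 0.84674 = 0.055, which is 6.1% of go results. By minimum likelihood 18/44 is significant and no power is lost.

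**5. Expansion.** At 100 patients against 5%, the doubled-tail test first rejects at 11 responses (p = 0.0564 at 10 and 0.0229 at 11). Its power at 30% exceeds 0.999, so the gap disappears.

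**The case against.** The strongest reply is that nothing stated is wrong. Both documents print alpha and power beside the boundaries they describe, under sample-size headings, and claim no power for the exact test. The go boundary only says that further investigation may be warranted, and no passage equates reaching it with significance. SAP 7.3 ties the Predictive Probability decision to the evaluable population, and the test has no decision role. All of this stands and is why the point is minor. It does not remove the gap: the design promises power of at least 0.90 against p0, and the only test of p0 that will be reported does not have it at 17 patients.

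Three limits also stand. Cohort 2 depends on the p-value definition, which may be given in the separate table shells that the SAP cites. The counts hold only at 17 and 44 evaluable patients, and the stopping rules are to be recalculated for the actual Stage 1 size. The denominators follow SAP 12.5.1 (evaluable population), whereas Protocol 9.3.1 names the mITT population, where they can differ.

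A reader might infer more: that 0.9045 and 0.9018 are errors, that false positives are inflated, or that all four cohorts certainly lose power. The documents support none of these. The figures reproduce exactly, the test is stricter than the go rule, and the Cohort 2 loss is conditional.

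**Conclusion.** The concern holds, as a minor point. In Cohorts 1, 3 and 4 at 17 evaluable patients it does not depend on how the exact p-value is formed: the test needs 4/17, and its power at a 30% ORR is 0.790 against 0.9045 for the go rule. In Cohort 2 at 44 patients, power is 0.847 against 0.9018 if the p-value is the doubled tail or is read from the Clopper-Pearson interval, with no loss under minimum likelihood.

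The figures assume Stage 1 of exactly 9 and 17 patients, the planned continuation rules, and the same responses and denominators for the go decision and the final test. They do not apply to Cohort 3 or 4 if it is expanded towards 100. The mismatch affects one response count per cohort and does not change enrolment or the go rule.

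**What to change.** Amend SAP 12.5.1 in the final SAP, which SAP 4.0 schedules before database lock. Protocol 9.4.1 already leaves further details to the SAP.

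1. Name the two-sided p-value definition. The doubled tail agrees with the planned Clopper-Pearson interval. Fixing it before the results also removes a choice that could reverse the Cohort 2 conclusion at 18/44.
2. State that the 0.90 power belongs to the go rule, and that at the planned sizes the reported test needs 4/17 and 19/44, with power of about 0.79 and 0.85. Recompute these for the actual evaluable numbers.
3. State that meeting the go boundary does not imply significance at two-sided 5%.

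The cost is a few sentences and a less favourable stated power, with no extra patients. If Protocol 9.4.1 is edited as well, Protocol 13.1 requires an amendment or administrative letter and IRB/EC submission. A SAP-only change avoids that.
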